## **7.2. Prohibited Medications and Non-Drug Therapies**

Subjects must abstain from using investigational and prohibited prescription or non-prescription drugs within 7 days or 5 half-lives (whichever is longer) prior to the first dose of study treatment and until completion of follow-up procedures unless in the opinion of the investigator and sponsor the medication will not interfere with the study (Section 4.1. Subject Selection Criteria).

The following medications are prohibited or permitted only with restricted use (as outlined below) during the study:

- Any other TPO-R agonists, without exception.
- Deferasirox shares some aspects of the safety profile of eltrombopag (e.g., hepatic abnormalities, renal tubular toxicity in mice and rats, cataract development in young rodents, and inhibition/metabolism of the enzymes CYP2C8, CYP1A2, UGT1A1 and UGT1A3). Therefore, use of this medication is permitted, if a subject is already taking deferasirox at the time of study entry. **No new treatment with deferasirox should be initiated while on study medication.** Continuation of deferasirox is permitted only if any potential deferasirox-related safety events have clearly been documented, and the continuation of deferasirox is deemed clinically important by the investigator. These measures should allow for a better identification of potential eltrombopag-related events without confounding by deferasirox. According to published treatment guidelines, iron chelation therapy with deferasirox should not be considered in patients with advanced MDS and AML [Bennett, 2008].

### **7.3. Treatment after Discontinuation of Study Treatment or withdrawal from/Completion of Study**

The investigator is responsible for ensuring that consideration has been given for the post-study care of the subject's medical condition whether or not Novartis is providing specific post-study treatment.

Post-study treatment will not be provided as part of the protocol. Upon discontinuation from study treatment, subjects may receive additional (non-protocol) therapy at the discretion of the treating physician. New therapy should be documented in the eCRF. Every effort should be made to complete the required post-treatment follow-up evaluations prior to initiating further anti-cancer therapy or dosing of an investigational agent (see Appendix 1) for Final Study Visit assessments and procedures.

### **7.4. Treatment of Study Treatment Overdose**

For the purposes of this study, an overdose of eltrombopag is defined as any dose greater than the highest daily dose allowed in the parent study.

In cases of suspected or confirmed overdose with eltrombopag, consider oral administration of a metal cation-containing preparation, such as calcium, aluminum, or magnesium preparations to chelate eltrombopag and thus limit absorption. Closely monitor platelet counts. Hemodialysis is not expected to enhance the elimination of eltrombopag because eltrombopag is not significantly renally excreted and is highly bound to plasma proteins.

No specific antidote is known. A hematologist will be consulted and appropriate treatments will be determined

## **8. STUDY ASSESSMENTS AND PROCEDURES**

A signed, written informed consent form must be obtained from the subject (or subject's legally acceptable representative) prior to any study-specific procedures or assessments.

Refer to the Time and Events Table (Appendix 1) for the timing of all study specific assessments and procedures. Further details of study procedures and assessments can be found in the study procedures manual (SPM).

Investigators may be requested to perform additional safety tests during the course of the study based on newly available data to ensure appropriate safety monitoring.

Appropriate local regulatory and ethical approvals should be obtained before any additional testing is performed.

Cardiovascular medical history/risk factors will be assessed at baseline.

### **8.1. Transition Visit**

For this study, the Transition Visit must occur within 28 days of the last day of study treatment of the parent study and may be on the same day as the last study treatment visit of the parent study. The results of any specified study assessments performed on the day of the Transition Visit will serve as the baseline value for the said assessment.

At the Transition Visit, the following assessments will be performed once a signed, written consent form for the study 200170 has been obtained from the subject or the subject's legally acceptable representative (prior to any study specific procedures or assessments). Pediatric subjects over 6 years old will be asked to sign an assent form as appropriate per local regulations.

- Demographic data, including date of birth, sex, ethnicity and race.
- Subject-related data from parent study, including parent study protocol number, parent study subject treatment number, previous subject number assigned in the parent study, start date and dose of eltrombopag treatment, dose of eltrombopag at the time of transition to this study; and best response based on last disease assessment in parent study for MDS/AML subjects.
- Complete physical examination.
- 12 lead ECG.
- Clinical laboratory tests: hematology and clinical chemistry as listed in Table 5.
- Documentation of ongoing AEs and SAEs at the time of transition to the rollover study.
- Review of concomitant medications.
- Review and record any blood and blood supportive care products.
- Documentation of bone marrow examination if performed, including cytomorphology and cytogenetic assessment when performed per SOC and/or disease progression.

## **8.2. Continuous Dosing Treatment Period**

The following assessments must be performed at each Treatment Visit as per the Time and Events Table (Appendix 1).

- Complete physical examination.
- Clinical laboratory tests: hematology and clinical chemistry as listed in Table 5.
- Documentation of AEs and SAEs.
- Review of concomitant medications.
- Documentation of bone marrow examination if performed, including cytomorphology and cytogenetic assessment when performed per SOC and/or disease progression.
- Document disease response in MDS/AML subjects only if assessed as per SOC.
- Document disease progression in MDS/AML subjects only if assessed as per SOC.
- Review and record any blood and blood supportive care products.

## **8.3. Final Study Visit**

If the subject is withdrawn from study treatment or has completed the study, the following assessments will be performed within 30 days (+ 7 days) from the last dose of study treatment and prior to initiating any other investigational product:

- Complete physical examination.
- Clinical laboratory tests: hematology and clinical chemistry as listed in Table 5.
- Documentation of bone marrow examination if performed as part of standard care, including cytomorphology and cytogenetic assessment.
- Documentation of AEs and SAEs.
- Document disease response for MDS/AML subjects only.
- Document disease progression for MDS/AML subjects only.
- Review and record any blood and blood supportive care products.

## **8.4. Safety**

Measurements used to evaluate safety will include physical exams, clinical laboratory tests (hematology and clinical chemistry), and monitoring of AEs/SAEs. Planned study visits for all safety assessments are listed in the Time and Events Table (Appendix 1).

Additional, unplanned safety assessments may be performed during the course of the study as clinically indicated at the judgment of the investigator. Additional safety tests may be added during the course of the study based on newly available data to ensure appropriate safety monitoring.

NOTE: The term ‘baseline’ will refer to the value obtained on the date of the first dose of study treatment following transition to the rollover study and does not refer to the ‘baseline’ value recorded for the same assessment in the parent study.

#### 8.4.1. Physical Examination

A complete physical examination will be performed at the visit schedule as outlined in Figure 1 and the Time and Events Table (Appendix 1).

#### 8.4.2. Bone Marrow Examinations

Disease status may be evaluated in part by means of periodic bone marrow examinations throughout the study, as per SOC and should be considered for subjects who have disease progression.

Information from bone marrow examinations that are performed during the study should be entered in the eCRF. Bone marrow cytomorphology and cytogenetic assessment should also be entered in the eCRF if collected.

#### 8.4.3. Laboratory Assessments

Clinical laboratory tests (Table 5) will be performed as outlined in the Time and Events Table (Appendix 1). At the discretion of the investigator, additional laboratory samples may be taken as clinically necessary.

Local laboratories will be used for hematology and chemistry assessments. Local laboratory reference ranges for all safety parameters should be provided to Novartis by the site **prior** to receiving study medication shipment.

**Table 5 Laboratory Assessments**

Hematology	Standard Chemistry
Hemoglobin	Blood urea nitrogen or urea
Hematocrit	Creatinine
Red blood cell count	AST
Platelets	ALT
White blood cell count with differential	Total bilirubin
Total neutrophils	Direct bilirubin
Lymphocytes	Albumin
Monocytes	Pregnancy
Eosinophils	Serum $\beta$ -hCG (human chorionic gonadotrophin)
Basophils	
Blast % from peripheral blood smear 	

1. Subjects from Cohort A only

2. Before the first dose of study treatment (-14 days) and at the investigator discretion

#### 8.4.4. Adverse Events

The investigator or site staff will be responsible for detecting, documenting and reporting events that meet the definition of an AE or SAE as outlined in Section 8.4.4.1.

Adverse event and serious adverse events will be reported in accordance with the Common Terminology Criteria for Adverse Events (CTCAE) v4.0 toxicity grades. The general guidelines for this toxicity grading system are as follows:

- Grade 1 - Mild; asymptomatic or mild symptoms; clinical or diagnostic observations only; intervention not indicated.
- Grade 2 - Moderate; minimal, local or non-invasive intervention indicated; limiting age appropriate instrumental activities of daily living.
- Grade 3 - Severe or medically significant but not immediately life-threatening; hospitalization or prolongation of hospitalization indicated; disabling; limiting self-care activities of daily living.
- Grade 4 - Life threatening consequences; urgent intervention indicated.
- Grade 5 - Death related to AE

#### **8.4.4.1. Definition of an AE**

Any untoward medical occurrence in a subject or clinical investigation subject, temporally associated with the use of a medicinal product, whether or not considered related to the medicinal product.

Note: An AE can therefore be any unfavorable and unintended sign (including an abnormal laboratory finding), symptom, or disease (new or exacerbated) temporally associated with the use of a medicinal product. For marketed medicinal products, this also includes failure to produce expected benefits, abuse, or misuse. Examples of events meeting the definition of an AE include:

- Exacerbation of a chronic or intermittent pre-existing condition including either an increase in frequency and/or grade of the condition.
- New conditions detected or diagnosed after study treatment administration even though it may have been present prior to the start of the study.
- Signs, symptoms, or the clinical sequelae of a suspected interaction.
- Signs, symptoms, or the clinical sequelae of a suspected overdose of study treatment (overdose per se will not be reported as an AE/SAE unless this is an intentional overdose taken with possible suicidal/self-harming intent. This should be reported regardless of sequelae).

The signs and symptoms and/or clinical sequelae resulting from lack of efficacy will be reported if they fulfill the definition of an AE or SAE. Also, “lack of efficacy” or “failure of expected pharmacological action” also constitutes an AE or SAE.

Events that **do not** meet the definition of an AE include:

- Medical or surgical procedure (e.g., endoscopy, appendectomy); the condition that leads to the procedure is an AE.
- Situations where an untoward medical occurrence did not occur (social and/or convenience admission to a hospital).

- Anticipated day-to-day fluctuations of pre-existing disease(s) or condition(s) present or detected at the start of the study that do not worsen.
- The disease/disorder being studied, or expected progression, signs, or symptoms of the disease/disorder being studied, unless more severe than expected for the subject's condition.

#### **8.4.4.2. Definition of a SAE**

A serious adverse event is any untoward medical occurrence that, at any dose:

a. Results in death

NOTE: Death due to disease under study is to be recorded on the Death eCRF form and does not need to be reported as an SAE.

b. Is life-threatening

NOTE: The term 'life-threatening' in the definition of 'serious' refers to an event in which the subject was at risk of death at the time of the event. It does not refer to an event, which hypothetically might have caused death, if it were more severe.

c. Requires hospitalization or prolongation of existing hospitalization

NOTE: In general, hospitalization signifies that the subject has been detained (usually involving at least an overnight stay) at the hospital or emergency ward for observation and/or treatment that would not have been appropriate in the physician's office or out-patient setting. Complications that occur during hospitalization are AEs. If a complication prolongs hospitalization or fulfills any other serious criteria, the event is serious. When in doubt as to whether "hospitalization" occurred or was necessary, the AE should be considered serious.

Hospitalization for elective treatment of a pre-existing condition that did not worsen from baseline is not considered an AE.

d. Results in disability/incapacity, or

NOTE: The term disability means a substantial disruption of a person's ability to conduct normal life functions. This definition is not intended to include experiences of relatively minor medical significance such as uncomplicated headache, nausea, vomiting, diarrhea, influenza, and accidental trauma (e.g. sprained ankle) which may interfere or prevent everyday life functions but do not constitute a substantial disruption.

e. Is a congenital anomaly/birth defect.

f. Medical or scientific judgement should be exercised in deciding whether reporting is appropriate in other situations, such as important medical events that may not be immediately life-threatening or result in death or hospitalization but may jeopardize the subject or may require medical or surgical intervention to prevent one of the other outcomes listed in the above definition. These should also be considered serious. Examples of such events are invasive or malignant cancers, intensive treatment in an emergency room or at home for allergic bronchospasm, blood

dyscrasias or convulsions that do not result in hospitalization, or development of drug dependency or drug abuse.

g. Protocol-Specific SAEs

- All events of possible drug-induced liver injury with hyperbilirubinaemia defined as ALT  $\geq$  3xULN **and** bilirubin  $\geq$  2xULN (>35% direct) (or ALT  $\geq$  3xULN and INR>1.5, if INR measured) termed 'Hy's Law' events (INR measurement is not required and the threshold value stated will not apply to patients receiving anticoagulants).
- NOTE: bilirubin fractionation is performed if testing is available. If testing is unavailable, record presence of detectable urinary bilirubin on dipstick indicating direct bilirubin elevations and suggesting liver injury. If testing is unavailable and a subject meets the criterion of total bilirubin  $\geq$  2xULN, then the event is still reported as an SAE. If INR is obtained, include values on the SAE form. INR elevations >1.5 suggest severe liver injury.

**8.4.4.3. Laboratory and Other Safety Assessment Abnormalities Reported as AEs and SAEs**

Any abnormal laboratory test results (hematology, clinical chemistry, or urinalysis), or other safety assessments (e.g., ECGs, radiological scans, vital signs measurements) including those that worsen from baseline, and events felt to be clinically significant in the medical and scientific judgment of the investigator are to be recorded as an AE or SAE, in accordance with the definitions provided.

In addition, an associated AE or SAE is to be recorded for any laboratory test result or other safety assessment that led to an intervention, including permanent discontinuation of study treatment, dose reduction, and/or dose interruption/delay.

Any new primary cancer must be reported as an SAE.

However, any clinically significant safety assessments that are associated with the underlying disease, unless judged by the investigator to be more severe than expected for the subject's condition, are not to be reported as AEs or SAEs.

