#### **5.4.1.2. Dose Reduction**

Subjects whose platelet count exceeds 400 Gi/L at any point during the treatment period must decrease the dosage of study medication. Temporary dose reduction of study medication may also be made by the investigator (i.e. to allow for recovery of AEs) as per Table 1 and Section 5.4.1.3.

If a subject's platelet count increases significantly and if the investigator thinks a dose reduction is medically appropriate, the dose can be decreased even if the platelet count is below 200 Gi/L or a dose modification was done less than 2 weeks before.

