#### **5.4.2.2. Dose Reduction**

If the platelet count exceeds 200 Gi/L, the dose of eltrombopag will be decreased as outlined in Table 2, Table 3 or Table 4.

If a subject requires a dose lower than the available tablet strengths or between 2 available tablet strengths, alternate dosing regimens that modify the frequency of administration may be used.

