#### **5.4.2.3. Dose Interruption**

If the platelet count exceeds 400 Gi/L, the dose of eltrombopag will be interrupted until the platelet count  $< 150$  Gi/L. At that point, eltrombopag will be reinitiated at the next lower dose or frequency.

If the platelet count is still above 150 Gi/L within one week after study treatment interruption, the platelet count needs to be monitored 3-4 days later, and twice a week until the platelet count is  $\leq 150$  Gi/L. Once the subject's platelet count is  $\leq 150$  Gi/L, study treatment should be started at the next lower dose or frequency.

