### **2.7.1 Adverse events (AEs)**

Summary tables for adverse events (AEs) will include only AEs that started or worsened during the on-treatment period, the *treatment-emergent* AEs.

AEs will be summarized by number and percentage of subjects having at least one AE, having at least one AE in each primary system organ class (SOC) and for each preferred term (PT) using the latest version of the medical dictionary for regulatory activities (MedDRA) at the time of the analysis for coding. A subject with multiple occurrences of an AE will be counted only once in the respective AE category. A subject with multiple CTCAE grades for the same preferred term will be summarized under the maximum CTCAE grade recorded for the event.

In AE summaries, the primary system organ class (SOC) will be presented alphabetically and the preferred terms (PT) will be sorted within primary SOC in descending frequency. The sort order for the preferred term will be based on descending frequency.

The following AE summaries will be produced:

- All AEs regardless of relationship to study treatment by primary system organ class (SOC), preferred term (PT) and maximum severity
  - In-text table by SOC and maximum severity
  - In-text table by PT and maximum severity
- AEs suspected to be related to study treatment by SOC, PT and maximum severity
  - In-text table by PT and maximum severity
- AEs leading to treatment discontinuation regardless of relationship to study treatment by SOC, PT and maximum severity
  - In-text table by PT and maximum severity
- Serious AEs (SAEs) regardless of relationship to study treatment by SOC, PT and maximum severity
  - In-text table by PT and maximum severity
- On-treatment deaths by SOC and PT
  - In-text table by PT
- \*Non-SAEs regardless of relationship to study treatment (threshold=x%) by SOC and PT
- \*On treatment deaths and SAEs by SOC and PT

\*For the legal requirements of EudraCT, two required tables on on-treatment/treatment emergent AEs which are not SAEs with an incidence greater than x% and on on-treatment/treatment emergent SAEs and SAE suspected to be related to study treatment will be provided by SOC and PT on the ATS.

If for a same patient, several consecutive AEs (irrespective of study treatment causality, seriousness and severity) occurred with the same SOC and PT:

- a single occurrence will be counted if there is  $\leq 1$  day gap between the end date of the preceding AE and the start date of the consecutive AE

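### Read literally, the AE rule captures platelet-driven dose reductions and interruptions, and the SAP's subject-level AE totals do not separate them

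*Protocol*

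**What the plan says.** **Recording rule.** Protocol 8.4.4.3 first asks for abnormal or clinically significant results to be recorded in line with the AE and SAE definitions. It then adds that "an associated AE or SAE is to be recorded for any laboratory test result or other safety assessment that led to an intervention". The scope of that last word is spelled out as "including permanent discontinuation of study treatment, dose reduction, and/or dose interruption/delay". Left out of reporting by the same section are "any clinically significant safety assessments that are associated with the underlying disease, unless judged by the investigator to be more severe than expected".

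**Platelets as a safety test.** Protocol 8.4 states: "Measurements used to evaluate safety will include physical exams, clinical laboratory tests (hematology and clinical chemistry), and monitoring of AEs/SAEs". Table 5 lists platelets under hematology.

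**Titration.** For ITP, Protocol 5.4.2.2 says: "If the platelet count exceeds 200 Gi/L, the dose of eltrombopag will be decreased". Protocol 5.4.2.3 says: "If the platelet count exceeds 400 Gi/L, the dose of eltrombopag will be interrupted". For MDS/AML, Protocol 5.4.1.2 says: "Subjects whose platelet count exceeds 400 Gi/L at any point during the treatment period must decrease the dosage of study medication".

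**Analysis.** SAP 2.7.1 summarises all treatment-emergent AEs by system organ class (SOC), preferred term (PT) and maximum severity, and separately "AEs suspected to be related to study treatment by SOC, PT and maximum severity". Each subject counts once per AE category. For the EudraCT tables, episodes of the same term more than one day apart are separate occurrences. SAP 2.7 displays the summaries by cohort. SAP 2.5 makes safety the primary objective.

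**The concern.** The AE tables are the main result of this study, and a reader will take them as a record of harm over long treatment. Eltrombopag is given to raise platelets, and the protocol expects the dose to be lowered when the count goes too high. If each such adjustment generates an AE record, the totals mix dose-finding with toxicity. The SAP has no table that reports the totals without these records.

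Consistency is also at stake. The protocol does not say whether routine titration is an intervention for the AE rule, so two sites could record the same event differently. By April 2016, 21 treated patients were spread over 11 countries, about two per country (21/11 = 1.9). With so few subjects per country, different readings could affect the observed rates.

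**Working it through.** The plan gives no titration frequency, AE rate or calculated sample size for this point, so there is no figure to reproduce. The check is mainly textual, with short arithmetic on size.

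**Step 1. Does the rule reach titration?** The trigger in 8.4.4.3 is a laboratory result that led to an intervention, and dose reduction and interruption are named. Platelets are a protocol laboratory test (8.4, Table 5). A high count leads to one of these actions at the following thresholds:

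| Population | Count | Action | Source |
|---|---|---|---|
| ITP | above 200 Gi/L | reduce | 5.4.2.2 |
| ITP | above 400 Gi/L | interrupt | 5.4.2.3 |
| MDS/AML | above 400 Gi/L | reduce | 5.4.1.2, Table 1 |

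On its wording, the rule applies.

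**Step 2. Does anything exempt high counts?**
- The exclusion in 8.4.4.3 concerns findings tied to the underlying disease. A high count on drug is not, on its face, such a finding.
- Protocol 8.4.4.6.2 treats thrombocytopenia needing rescue as treatment failure. That covers low counts only.
- Protocol 5.4 describes adjustment to platelet response separately from adjustment for safety assessments. The AE rule does not carry that distinction over.
- Table 2 note 3 and Table 3 note 4 let the investigator keep the dose at 200 to 400 Gi/L. With no dose change the rule is not triggered, so crossing the threshold need not produce an AE.

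**Step 3. Where do the records go?** They can enter the any-AE total, the SOC total, the PT row and the EudraCT occurrence counts. They enter the related-AE table only if the investigator suspects a relationship.

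The PT row does not allow the totals to be corrected. If A subjects have any AE and B subjects appear in the platelet-increase row, the total without titration-only events lies anywhere from A − B to A. The tables do not show which of the B subjects had other AEs, or which events had no consequence beyond a dose change.

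**Step 4. Size.** SAP section 1 gives 22 subjects, and SAP 2.1 places them in Cohorts A and B only.
- Overall, one subject whose only AE is a titration event adds 1/22 = 4.5 percentage points.
- By cohort, if both cohorts hold subjects, the smaller has at most 11. One such subject there adds at least 1/11 = 9.1 points.

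The following is an illustration only. All inputs are assumed and taken as independent:
- p = share of subjects with some other AE;
- r = share with some other related AE;
- q = share with a platelet-driven reduction or interruption that is recorded as an AE;
- c = chance that the investigator calls it related.

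Rise in any-AE rate = (1 − p)q:
- p = 0.9, q = 0.1: 0.1 × 0.1 = 0.01, or 1 point;
- p = 0.5, q = 0.5: 0.5 × 0.5 = 0.25, or 25 points.

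Rise in related-AE rate = (1 − r)qc:
- c = 0: 0 points;
- c = 1, r = 0.4, q = 0.1: 0.6 × 0.1 = 0.06, or 6 points;
- c = 1, r = 0.1, q = 0.5: 0.9 × 0.5 = 0.45, or 45 points.

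The width of these ranges shows that the documents do not fix the size.

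**The case against.** **A site could reasonably have left titration out.** The heading of 8.4.4.3 speaks of abnormalities, its first paragraph refers back to the AE definitions, and 8.4.4.1 defines an AE as an untoward event. With the distinction in 5.4, that reading is available. This stands, and it means the text is unreconciled. It does not remove the problem: the sentence on interventions is an addition to the first paragraph and covers any result.

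**Overshoot may be a real safety signal.** The ITP target is 50 to 200 Gi/L, the risk management plan lists thromboembolic events as an identified risk, and Protocol 10.3.4.1.1 names thromboembolism as an AE of special interest. Recording a count that forces a dose change is a defensible cautious choice. This also stands, and it is why no record should be removed.

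**The events are visible.** PT rows, the listing of all AEs, the laboratory listings and the table of platelet counts over time will show them. A reader might infer that nothing in the output identifies these events, and that would be wrong. What is missing is a subject-level total without them.

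**Drug-related rates.** A reader might infer that these must be inflated. The documents do not support that, because the rule does not set causality. Attribution to eltrombopag is plausible, since the drug raises platelets, but it is left to the investigator.

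**Projection from visits.** A reader might try to project the share of subjects affected from an assumed chance per visit of crossing a threshold. The documents give neither that chance nor the number of visits. Visits are not independent, because a reduction is meant to lower later counts, and the cohorts have different thresholds. The result would be the share crossing a threshold, not the rise in the any-AE rate.

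**No comparison is at risk.** The study is single-arm and descriptive, so no test or between-arm contrast is biased. This limits the consequence to how the descriptive rates are read.

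**Conclusion.** The point holds as a gap between the AE rule and the titration scheme that the SAP does not resolve. Followed literally, the protocol makes a platelet result that leads to a directed reduction or interruption a recordable AE. It does not follow that every titration was recorded, or that every threshold crossing led to one. The effect on the any-AE and SOC totals is limited to subjects with no other AE in that category. Occurrence counts can accumulate with repeated episodes.

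The firm figures are 4.5 points per affected subject overall and at least 9.1 points in the smaller cohort, if both cohorts are populated. How many subjects are affected cannot be learned from the documents. The conclusion rests on reading the sentence on interventions in 8.4.4.3 as written.

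**What to change.** Keep all AE records. In SAP 2.7.1, present the all-AE and related-AE tables, or at least the any-AE, SOC and occurrence totals, twice: with all events, and without platelet-count-increase events that were non-serious, had no symptoms, and whose only action was a dose change under Protocol Tables 1 to 4.

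The material for this appears to be available. Protocol 5.9 puts dates of dose reductions and delays in the eCRF, and Protocol 10.3.4.1.1 foresees summarising the action taken for AEs of special interest. With 22 subjects, the qualifying records can be identified individually. The selection rule should be written down before database lock. If lock has passed, label the tables as post hoc in the study report.

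Rewording 8.4.4.3 would no longer change what sites record, because the last patient's last visit was on 23-Feb-2022, before SAP Amendment 2 of 08-Mar-2022. Instead, state in the SAP and the study report that 8.4.4.3 and the titration passages were not reconciled during conduct and that sites may have recorded such events differently. The repeat tables cannot correct uneven recording, so this statement is needed as well.

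The cost is a few repeat tables, a short record review and one paragraph of text.
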